7. NOTATION OF TREATMENT GROUPS AND VISITS

Table 7.1.1 Notation of Treatment Groups

The following notation of treatment groups will be used throughout the report:

Full notation (as used in the study protocol)	Notation used throughout all tables, listings, and figures
300 mg oral omadacycline	Omadacycline 300 mg
Placebo	Placebo

Table 7.1.2 Visit Terminology

Visit	Notation used throughout all tables, listings, and figures
Screening	Screening
Day 1 Baseline	Day 1 (in Listings)/ Baseline (in Tables and Figures)
Day 14 Tele-visit (\pm 2d)	Day 14
Day 28 (\pm 3d)	Day 28

Day 56 ($\pm 3d$)	Day 56
Day 84 (+5d/-2d)	Day 84
EOT: defined as the visit occurring when subjects prematurely discontinue treatment (End of Treatment) (+5d/-2d)	EOT (shown on listings)
Day 84/EOT: defined as Day 84 for subjects who complete treatment or the visit occurring when subjects prematurely discontinue treatment (End of Treatment) (+5d/-2d)	Day 84/EOT (shown on tables)
30 Day Safety Follow-up Call (+7d)	Follow-up

EOT = end of treatment

For by visit summaries, the nominal visit will be summarized. If there is no nominal visit result, unscheduled visits that occur in the protocol defined window will be summarized instead. If multiple unscheduled visits occur in the window, the one closest to the nominal visit date will be used. For sputum cultures, if there are multiple positive cultures on the same day with different MICs to omadacycline, the culture with the highest MIC to omadacycline is used.

Study days corresponding to measurements are calculated as:

- Assessment date – date of first exposure to treatment + 1 (if assessment date is on or after the date of first exposure to treatment)
- Assessment date – date of first exposure to treatment (if assessment date is before the date of first exposure to treatment)

If the date of first exposure to treatment is missing, study days will be calculated by using the randomization date.

8. ANALYSIS SETS

The following subject population will be used for safety analyses:

- The safety analysis set will include all subjects who received at least 1 dose of test article. Treatment assignment will be based on the actual test article received the majority of time while on treatment.

The following subject populations will be used for efficacy analyses:

- The intent-to-treat (ITT) analysis set will include all randomized subjects. Treatment assignment will be based on the randomized treatment.
- The per-protocol (PP) analysis set will include all randomized subjects who received at least 1 dose of test article and completed the study without major protocol deviations that affect the assessment of efficacy. The decision whether a subject is excluded from the PP analysis set will be made prior to database lock and unblinding. Treatment assignment will be based on randomized treatment.

9. STUDY CONDUCT

9.1 Subject Disposition

Subject disposition information will be summarized for all subjects by treatment group and overall. The number and percentage of subjects who are screened, randomized, subjects in each analysis set for all subjects and the number and percentage of subjects who complete treatment, subjects who prematurely discontinued test article and the reason for discontinuation, the number and percentage of subjects who complete the study as well as the number and percentage of subjects prematurely discontinuing the study and the primary reason for discontinuation will be presented by treatment group in the ITT analysis set.

A listing of all subjects who prematurely discontinued from test article and the reasons for discontinuation and all subjects who prematurely discontinued from the trial and the reasons for discontinuation will be presented.

9.2 Protocol and Good Clinical Practice (GCP) Deviations

A protocol deviation is any change, divergence, or departure from the study design or procedures defined in the protocol that may be on the part of the Investigator, site personnel, or the subject. GCP deviation is any breach from GCP standards due to various reasons, including human error, technical glitches, or unforeseen circumstances.

Major protocol and GCP deviations are a subset of protocol and GCP deviations that may significantly impact the completeness, accuracy, and/or reliability of the study data or that may significantly affect a subject's rights, safety, or well-being.

All protocol and GCP deviations, including the deviation designation (major or minor), category, and indication of whether the deviation led to an exclusion of a subject from the PP analysis set, will be presented in a data listing.

The number and percentage of subjects with any protocol and GCP deviation, with at least one minor, and with at least one major deviation will be summarized by treatment group in the ITT analysis set. Major protocol deviations will also be summarized by deviation category and treatment group in the ITT analysis set.

9.3 Eligibility

A listing of subjects in the ITT analysis set not fulfilling any eligibility criteria will be provided.

9.4 Prior and Concomitant Medications

Prior and concomitant medication verbatim terms in the eCRFs will be mapped to the World Health Organization (WHO) Anatomical Therapeutic Chemical (ATC) classification and preferred names using the WHO Drug Global dictionary B3 format, version March 2021.

Partial dates will be imputed. For details on imputation rules, refer to [Appendix A: Presentation of Data and Programming Specifications](#). Imputed dates are only used for classification of a medication as a prior or concomitant medication; no other calculation, such as durations, will be done.

Prior medications are defined as any medication with a start date before the start date of test article. Concomitant medications are defined as any medication that was started before the start date of test article and with a stop date on or after the start date of test article or are considered ongoing, or that are started on or after the start date of test article. Medications can be considered both prior and concomitant. If the medication cannot be classified as a prior or concomitant medication, the medication will be considered as concomitant.

Medications will be summarized for each treatment group by level 4 ATC class (where applicable) and preferred name. These summaries will present the number and percentage of subjects using each medication. Subjects may have more than 1 medication per ATC class (where applicable) and preferred name. At each level of subject summarization, a subject is counted once if he/she reported 1 or more medications at that level. Each summary will be ordered by descending subject count in the total column by ATC level (where applicable) and preferred name. The following summaries will be provided:

- Prior antibiotics administered for MABc or MAC pulmonary disease in the ITT and Safety analysis sets
- Concomitant antibiotics administered for MABc or MAC pulmonary disease from the last dose of test article through the date of the end of the study in the ITT and Safety analysis sets
- Prior medications other than antibiotics administered for MABc or MAC pulmonary disease in the Safety analysis set
- Concomitant medications other than antibiotics administered for MABc or MAC pulmonary disease in the Safety analysis set.

10. DEMOGRAPHICS AND BASELINE CHARACTERISTICS

10.1 Demographics, Medical History and NTM Assessment

Demographics, baseline characteristics, medical history, and baseline assessment of NTM will be summarized by treatment group and overall.

The NTM Symptom Assessment Questionnaire asks subjects to rank the top three most bothersome symptoms on the scale at the baseline visit. Each symptom will be scored with 3 points for a top rating, 2 points for a second-place rating, and 1 point for a third place-rating. Each symptom will be summed within treatment group and this sum will be presented on the baseline characteristics table with the symptom having the highest overall sum across treatment

groups appearing first to the symptom with the lowest score appearing last. This will be referred to as the NTM Baseline Symptom Bothersome Ranking.

The following demographic and baseline characteristics will be summarized for the ITT analysis set (except where indicated):

- Baseline demographics and characteristics: age as a continuous variable, age categorized as ≤ 65 and > 65 years, sex, ethnicity, race, height (cm), weight (kg), body mass index (BMI) (kg/m^2), by treatment group and overall. Baseline demographics and characteristics will be summarized for the ITT and safety analysis sets.
- The number and percentage of subjects in each randomization stratum (received prior treatment for NTM, did not receive prior treatment for NTM) based on the prior antibiotic data from the CRF will be presented by treatment group and overall. The table will also present the number and percentage of subjects with each severity category (absent, mild, moderate, severe) for the NTM symptoms at baseline from the NTM Symptom Questionnaire by treatment group and overall and in each randomization stratum. The Most Bothersome Symptom Ranking will also be presented by treatment group, overall and in each randomization stratum. The definition of the Most Bothersome Symptom Ranking is as the following. Subjects are asked to list up to 3 of their most bothersome symptoms at baseline. For each subject the number 1 mostly highly rated symptom will be given a score of 3, the second most highly rated will be given a score of 2, and the third most highly rated will be given a score of 1. Scores for each symptom will be tallied across all subjects. The symptom with the highest overall score will be considered most bothersome across the entire population, the second highest will be considered the second most bothersome for the entire population, etc..
- NTM disease history: duration of the MABC NTM pulmonary disease (defined as the number of days from the date of randomization to the first date of diagnosis of NTM pulmonary disease caused by MABC), if the subject had ever been diagnosed with NTM pulmonary disease caused by *Mycobacterium avium complex* (MAC), duration of NTM pulmonary disease caused by MAC (defined as the number of days from the date of randomization to the first date of diagnosis of NTM pulmonary disease caused by MAC), subjects with respiratory culture positive for MAC in the 6 months prior to screening, subjects having known chronic obstructive pulmonary disease (COPD), subjects having known bronchiectasis, the subject's smoking status (never smoked, former smoker and current smoker) and for former and current smokers, the length of smoking. For former smokers, length of smoking in years will be based on date started smoking to date stopped smoking + 1. For current smokers, length of smoking in years will be based on date started smoking to date of randomization + 1.
- Medical history: The verbatim term of the medical history condition/event will be coded using the Medical Dictionary for Regulatory Activities (MedDRA), Version 24.0.

Medical history will be summarized by treatment group and overall in the ITT and Safety analysis sets. The summary will show the system organ class (SOC) and preferred term (PT) ordered by descending subject count in the total column. Subjects will only be counted once for each SOC and for each PT within SOC.

10.2 Microbiology

10.2.1 Selection of Sample for Analysis

Sputum samples are collected at Screening, Baseline/Day 1, Day 28, Day 56 and Day 84/EOT. At least 2 and preferably 3 sputum samples are obtained at each time point. During Screening, samples will be collected after the subject signs the informed consent. For all subsequent visits, sputum samples should be collected on 2 to 3 consecutive days (when possible), just prior to, and up through the day of the scheduled visit.

The sputum specimens will be processed by a Central Specialty Microbiology Lab. Acid fast bacilli smear testing from sputum will be performed on all specimens received. Specimens will be further cultured in both solid and liquid media and identification of genus and species will be performed, to the subspecies level for *M. abscessus*.

In vitro susceptibility testing of antimicrobial drugs that may be used to treat *M. abscessus* pulmonary infection will be performed, and molecular characterization for select drug resistance markers will be performed.

Sputum samples noted to be of low volume will not be used for analysis unless all potential samples at a time point are of low volume. If all potential samples are of a low volume (signifying lower quality), the algorithms noted below for sample selection will be used.

For MIC susceptibility and outcome analyses of the MABC, the sample closest to but prior to the first dose of study drug (based on collection date and if on the same day as the first dose of study drug, collection date and time) which is positive for MABC is used as the baseline sample. If there are two samples positive for MABC with different subspecies, the one positive for *M. abscessus* subspecies *abscessus* is used. If multiple samples collected on the same day are positive for MABC, the sample positive for *M. abscessus* subspecies *abscessus* and with the highest MIC to omadacycline is considered the baseline sample. If the MICs are the same, the sample closest to the time of first dose of study drug based on time is used. The baseline samples for MAC and other species of mycobacterium (not *abscessus*) are defined in a similar manner and may or may not be the same sample as the one with MABC.

For post-baseline samples, a similar process is used for selecting the sample for analysis as that used for the baseline sample. The sample that is positive for MABC that is closest to the nominal/intended visit day should be selected.

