8.10 Sputum Collection For Microbiology

A Central Specialty Microbiology Laboratory will be used for analysis of all sputum specimens. Details on the collection supplies, shipment of samples and reporting of results are provided to investigators in the Central Laboratory Manual.

Pre-dose expectorated or induced sputum specimens (approximately 5 mL) will be collected at all timepoints as indicated in [Appendix 1](#). To improve the probability of obtaining a good sputum specimen, at least 2 and preferably 3 spontaneously expectorated sputum samples will be obtained from subjects at each timepoint. During Screening, samples will be collected after the subject signs the informed consent. For all subsequent visits, sputum samples should be collected on 2 to 3 consecutive days (when possible), just prior to, and up through the day of the scheduled visit.

If a subject is unable to produce sputum spontaneously and independently, sputum induction may be performed by appropriately qualified site staff to obtain one induced sputum specimen. Please refer to [Appendix 3](#). If a subject is still unable to produce sputum despite reasonable efforts at any visit post-Baseline, this will be considered as a negative culture result at that timepoint. Sterile, leak proof, non-wax, disposable plastic containers will be used to collect specimens. Detailed instructions will be provided by site staff to subjects on how to collect and handle samples aseptically to avoid contamination. Subjects will also be instructed to keep sputum samples refrigerated, not frozen, until ready to transport to the site. Upon receipt at the site, samples should be kept refrigerated until ready to ship to the central specialty microbiology lab. Shipping should occur within approximately 2 days of receipt from subject to avoid overgrowth by contaminating normal flora. No fixative or preservatives are to be used with sputum samples. Detailed instructions for collecting, processing, and shipping sputum specimens will be provided in the Central Laboratory Manual.

The Central Specialty Microbiology Lab will process the sputum specimens. Acid fast bacilli smear testing from sputum will be performed on all specimens received. Specimens will be further cultured in both solid and liquid media and identification of genus and species will be performed, to the subspecies level for *M. abscessus*. Results confirming *M. abscessus* infection will be used to verify subject eligibility during Screening.

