- For each definition of the primary endpoint, the number and percentage of subjects with a clinical response and who had culture conversion (ie, converted from a positive MABC sputum culture at baseline to a negative sputum culture at the Day 84 visit), clinical response and did not have culture conversion, clinical nonresponse and had culture

conversion, and clinical nonresponse and did not have culture conversion, will be presented by treatment group.

- The cumulative distribution of the change from baseline to the Day 84 visit in the respiratory domain of the QOL-B by PGI-S (categorized as improved vs. no change/worsened) will be provided as a graph.
- Descriptive statistics of the change from baseline to the Day 84 visit in the respiratory domain of the QOL-B in subjects who converted from positive MABC sputum culture at baseline to a negative sputum culture at the Day 84 visit, by treatment group will be presented.
- A subject will be defined as a responder if all 3 of his/her most bothersome symptoms at baseline are absent or mild at the Day 84 visit and a non-responder if at least one of the most bothersome symptoms is worse than mild. The number and percentage of subjects defined as a responder and nonresponder will be presented by treatment group.
- A sample is considered positive if there was any growth in broth or agar. A sample is considered negative if there was no growth in broth and agar.

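### SAP 10.2.1 drops a low-volume specimen that grew MABC when another specimen at the visit had adequate volume, so a visit with proven growth can be analysed as culture-negative

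*SAP*

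**What the plan says.** - **Number of specimens.** SAP 10.2.1: "At least 2 and preferably 3 sputum samples are obtained at each time point". Protocol 8.10 allows a single induced specimen for a subject who cannot expectorate.
- **Intended volume.** Protocol 8.10: "Pre-dose expectorated or induced sputum specimens (approximately 5 mL) will be collected at all timepoints as indicated in" the schedule. Neither document says below what volume a specimen counts as low.
- **Volume filter.** SAP 10.2.1: "Sputum samples noted to be of low volume will not be used for analysis unless all potential samples at a time point" fall short in the same way. The next sentence deals with that case: "If all potential samples are of a low volume (signifying lower quality), the algorithms noted below for sample selection will be used".
- **Post-baseline selection.** SAP 10.2.1: "The sample that is positive for MABC that is closest to the nominal/intended visit day should be selected".
- **Positive and negative.** SAP 12.3: "A sample is considered positive if there was any growth in broth or agar". SAP 12.2.11 calls a culture negative when neither broth nor agar grows MABC. Both definitions apply to one sample or culture, not to all the specimens of a visit.
- **Listings.** SAP 10.2.2 lists every sample and flags the selected one.

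**The concern.** Low volume is a reason to distrust a negative result, because organisms may have been missed. It is not a reason to set aside growth that the laboratory has identified as MABC. The filter treats both alike.

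Take a Day 84 visit with one adequate specimen that grows nothing and one low-volume specimen that grows MABC. The second is removed, the first is all that remains, and the subject is recorded as culture-negative at a visit where MABC was recovered. What is at stake is the accuracy of the culture-conversion and load endpoints, which carry the secondary microbiological objective.

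**Working it through.** **1. The plan's own figure.** The plan gives no number for this rule. Its one design figure is about 80% power for clinical response (15% v 45%, 30 placebo and 45 omadacycline, two-sided 0.05).
- Pooled rate: (0.45 × 45 + 0.15 × 30)/75 = 0.33.
- Null SE: √[0.33 × 0.67 × (1/45 + 1/30)] = 0.1108.
- Alternative SE: √[0.45 × 0.55/45 + 0.15 × 0.85/30] = 0.0987.
- Power: Φ[(0.30 − 1.96 × 0.1108)/0.0987] = Φ(0.84) ≈ 79.9%. Exact enumeration of the Mantel-Haenszel test gives 80.2%.

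The figure reproduces. It concerns the symptom endpoint, so the point below does not change it.

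**2. Order of the rules.** Low-volume specimens reach the selection algorithm only when every specimen at the time point is low-volume. Otherwise the preference for a positive specimen acts only on the adequate ones.

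**3. Which visits change.** Each specimen is adequate or low-volume, and grew MABC or did not: 4 states, hence 4^k patterns for k specimens. Compare SAP 10.2.1 with a rule that calls the visit positive if any specimen grew. They differ only when at least one specimen is adequate, all adequate ones are negative, and at least one low-volume one is positive. With a adequate specimens:

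N(k) = Σ (a = 1 to k−1) C(k,a) × (2^(k−a) − 1)

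| Specimens | Patterns | Changed |
|---|---|---|
| 1 | 4 | 0 (filter cannot act) |
| 2 | 16 | C(2,1) × 1 = 2 |
| 3 | 64 | C(3,1) × 3 + C(3,2) × 1 = 9 + 3 = 12 |

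Every changed pattern is negative under the SAP and positive when growth counts. The reverse cannot occur, because a visit that is positive under the SAP contains a specimen with growth. These are counts of patterns, not probabilities.

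**4. Effect on each endpoint.**
- **12.2.11, time to first negative culture.** The first negative is the event and needs no confirmation, so one misclassified visit can fix the event date.
- **12.2.10, time to growth in liquid medium only.** If no sample shows liquid-only growth, the first negative culture supplies the event date.
- **12.2.9, decrease in semi-quantitative score.** The baseline sample is chosen to be MABC-positive, so it scores at least 1 in the table in 10.2.2. A false negative scores 0 and therefore always counts as a decrease.
- **12.3, conversion summaries.** A false negative can create a conversion, or hide a later positive from the count of conversions by Day 56 with no subsequent positive culture. The table of clinical response by culture conversion inherits the error.

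**5. Is it corrected elsewhere?** The same-day rule in SAP Section 7 chooses among positive cultures by MIC. The listings show a discarded positive but do not return it to the analysis. Baseline is better protected, because it is the closest positive before the first dose and Screening can supply it. Each post-baseline visit stands alone.

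**The case against.** - **Another reading of the rule.** The potential samples could mean the MABC-positive candidates for the algorithm that follows, which would rescue a lone low-volume positive. The closing sentence of 10.2.1, which says to select the positive sample, lends this some support. But the filter is worded by time point and does not mention positivity. At best the text is ambiguous, and two programmers could code it differently.
- **Limited reach.** The filter does nothing when all specimens are low-volume or only one exists. If an adequate specimen is also positive, the visit stays positive; the rule then affects only which positive is scored, and that could move the score either way. This stands, and it limits how often the error can occur.
- **Exploratory setting.** The affected endpoints are secondary or additional, p-values are nominal, and the listings allow a check afterwards. This stands and limits the consequence, but a listing does not correct an estimate.
- **Bias towards omadacycline.** A reader might infer this because sputum production is a scored symptom and treatment may reduce it. The documents do not support it. It needs more mixed-volume visits in that arm, and no frequencies are given. A marked fall in sputum may instead give all-low or single-specimen visits, where the filter is idle. Misclassification also requires remaining MABC growth, which may be commoner on placebo.
- **Contradiction with SAP 12.3.** A reader might infer this too. That sentence defines a positive sample, and 10.2.1 chooses which sample is analysed. The two are compatible as written.
- **Number of specimens.** Fewer specimens give fewer chances to detect growth, but that follows from collection under Protocol 8.10, not from the volume filter. It is no part of this point.

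**Conclusion.** The point holds as a matter of rule logic. As written, SAP 10.2.1 can turn a post-baseline visit with proven MABC growth into a culture-negative visit with a score of 0. The misclassification runs only towards conversion or load decrease. It covers 2 of 16 two-specimen and 12 of 64 three-specimen patterns.

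This rests on two assumptions: that the filter is read by time point, as worded, and that the selected sample determines the visit result in 12.2.9 to 12.2.11 and 12.3. The share of visits affected cannot be derived from the documents, nor can any between-arm difference. Bias towards omadacycline would arise only if such mixed-volume visits were commoner in that arm. The primary endpoint and its power are untouched. The rule should be corrected because it gives a wrong result in an identifiable case and the data needed are already collected.

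**What to change.** Amend SAP 10.2.1 as follows:

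1. Apply the low-volume exclusion only to specimens without MABC growth.
2. Any specimen with MABC growth, of any volume, makes the visit positive for all culture endpoints.
3. For CFU and semi-quantitative score, use volume only to rank the MABC-positive specimens: take an adequate-volume positive if there is one, otherwise the low-volume positive, then apply the existing tie-breaks. A visit with growth then never scores 0. Keeping the exclusion for the score would leave a culture-positive visit counted as a load decrease under 12.2.9.
4. State the volume below which a specimen is low, before unblinding.
5. As supportive output, tabulate by arm and visit the number and type of specimens (spontaneous or induced, adequate or low-volume).

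The cost is SAP wording, one derivation change and one table, with no new samples. The reported conversion rate may be slightly lower. If the change is made after the blind is broken, SAP Section 6 requires the result to be labelled post hoc.
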